11. METHODS OF EFFICACY ANALYSIS

11.1 Primary Efficacy Analysis

The primary efficacy comparison will test the following hypotheses:

H_0 : The proportion of subjects with complete clearance is equal between SB206 12% QD and Vehicle;

H_1 : The proportion of subjects with complete clearance is different between SB206 12% QD and Vehicle.

The primary efficacy model will be the following for π_{H_i} as the probability of complete clearance for the i^{th} subject in household H:

$$\pi_{H_i} = \frac{e^{(\beta_0 + \beta_1 * X_{H_{i1}} + \beta_2 * X_{H_{i2}} + \beta_3 * X_{H_{i3}} + \beta_4 * X_{H_{i4}} + \beta_5 * X_{H_{i5}})}}{1 + e^{(\beta_0 + \beta_1 * X_{H_{i1}} + \beta_2 * X_{H_{i2}} + \beta_3 * X_{H_{i3}} + \beta_4 * X_{H_{i4}} + \beta_5 * X_{H_{i5}})}}$$

where H = Household, i = subject within the household, β_0 is the intercept,

$$X_{H_{i1}} = \begin{cases} 1, & \text{if treatment is SB206} \\ 0, & \text{if treatment is Vehicle} \end{cases}$$

$$X_{H_{i2}} = \begin{cases} 1, & \text{if subject is from a 2 subject household} \\ 0, & \text{if subject is from a 1 subject household} \end{cases}$$

$$X_{H_{i3}} = \begin{cases} 1, & \text{if subject is from a Dermatology site} \\ 0, & \text{if subject is from an Other site} \end{cases}$$

$X_{H_{i4}}$ is the subject's baseline lesion count, and $X_{H_{i5}}$ is the subject's age at baseline; treatment will be included in the class statement with PARAM=REF and REF=Vehicle. The working correlation will have an exchangeable structure. The model will include a repeated statement for subject household with household ID in the class statement. Also, the data structure will be ordered according to household ID and subject ID in household.

Treatment groups will be compared using a generalized estimating equation for logistic regression with an exchangeable working correlation structure. The model will include treatment, investigator type (dermatologist vs other), household number of randomly assigned subjects (1 subject per household vs 2 subjects per household), age, and baseline lesion count as factors. The odds ratio between SB206 12% and vehicle gel, 95% confidence intervals for the odds ratio, and P -value for the covariate-adjusted treatment comparison will be presented;

together with predicted proportions along with their associated 95% confidence interval. The difference in proportion confidence interval will be calculated using the following formula:

$$(p_{SB206} - p_{Vehicle}) \pm z_{0.025}^* * SE$$

Where the SE =

$$\sqrt{\frac{p_{SB206}^2(1-p_{SB206})^2 s_{SB206}^2 + p_{Vehicle}^2(1-p_{Vehicle})^2 s_{Vehicle}^2 - 2p_{SB206}(1-p_{SB206})p_{Vehicle}}{(1-p_{Vehicle}) * \left(\frac{s_{SB206}^2 + s_{Vehicle}^2 - s_{Odds\ Ratio}^2}{2} \right)}}$$

The p_{SB206} and $p_{Vehicle}$ are the transformed predicted log odds at the mean of the covariates, s^2 's are the standard errors of the predicted log odds and the odds ratio.

As a sensitivity analysis, the above primary analysis model will be applied to the PP Population. An additional sensitivity analysis counting subjects who discontinued prior to Week 12 or have a missing lesion count assessment but who demonstrated complete clearance at the last collected lesion assessment as responders will be presented. The impact of mis-stratifications may be explored via a sensitivity analysis.

An analysis where the complete clearance response probability for each dropout prior to Week 12 will be independently generated across the following scenarios (Vehicle response probability, SB206 response probability):

(0.1, 0.1)	(0.1, 0.0)			
(0.2, 0.2)	(0.2, 0.1)	(0.2, 0.0)		
(0.3, 0.3)	(0.3, 0.2)	(0.3, 0.1)	(0.3, 0.0)	
(0.4, 0.4)	(0.4, 0.3)	(0.4, 0.2)	(0.4, 0.1)	(0.4, 0.0)

The analysis will be produced 100 times and then the results for the estimated log odds ratio for treatment and its estimated standard error from each of the imputations will be combined using PROC MIANALYZE.

An additional sensitivity analysis will be performed in a subset of the ITT population where only 1 subject from each household is chosen to contribute to the model based on the subject with the highest number of baseline treatable MC and the oldest to break ties, if needed. A logistic regression model including treatment, investigator type, age, and baseline lesion counts will be utilized.

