5. DETERMINATION OF SAMPLE SIZE

Approximately 340 subjects, 6 months of age and older, with a minimum of 3 and a maximum of 70 MC lesions at Baseline will be randomized in a 2:1 (active:vehicle) scheme. The sample size assumptions for this study were informed by the completed Phase 2 study NI-MC201 of subjects 2 years of age and older with between 3 and 70 MC lesions at Baseline. In the Intent-to-Treat (ITT) Population of the Phase 2 study, the observed rates of complete clearance at Week 12 were 18% (12/66) for vehicle and 38% (18/48) for SB206 12% QD and the covariate-adjusted treatment difference was 18%.

A sample size of 340 subjects (227 subjects in the SB206 12% QD group and 113 subjects in the vehicle group) will provide 94% power for a 2-sided alpha test of size 0.05 to detect an absolute difference of 18% when the vehicle response rate is 18%. This same sample size provides 93% power to detect a treatment difference of 18% when the vehicle response rate is 20% and 83% power when the treatment difference is 15% and the vehicle response rate is 20%.

Since the intra-cluster correlation is estimated to be small (<10%) and the average size of households is expected to be capped at roughly 1.3, the sample size is still sufficient when considering the fact that the subjects within the household may not be independent.

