10.3 Adjustments for Covariates

The model for the primary efficacy will include adjustments for the following covariates: investigator type (dermatologist vs other), household number of randomized subjects (1 subject per household vs 2 subjects per household), age, and baseline lesion count. If there are not at least 3 responders and non-responders at each level of the stratification factors, then that stratification factor will be removed from the model. If there are fewer than 10 responders/non-responders, then neither investigator type nor household number of randomized subjects will be included in the model.

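### The model-predicted clearance proportions are evaluated at the mean of the covariates, so they do not estimate the proportion of subjects who clear; at the planned rates both arms are expected to come out low

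*Combined protocol and SAP*

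**What the plan says.** References are to the final SAP, the last of the three in the file.

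- **Model.** Section 11.1 compares the arms with a "generalized estimating equation for logistic regression with an exchangeable working correlation structure". Section 10.3 lists the covariates: "investigator type (dermatologist vs other), household number of randomized subjects (1 subject per household vs 2 subjects per household), age, and baseline lesion count".
- **Output.** Section 11.1 calls for the odds ratio, its 95% interval and the P-value, "together with predicted proportions along with their associated 95% confidence interval". It then gives a formula for the interval of the difference in proportions.
- **What is evaluated.** The two proportions in that formula "are the transformed predicted log odds at the mean of the covariates". No section averages predictions over subjects.
- **Target.** The null hypothesis in Section 11.1 reads "The proportion of subjects with complete clearance is equal between SB206 12% QD and Vehicle". Section 5 plans on subject proportions too: 18% or 20% on vehicle with differences of 18 or 15 points, informed by Phase 2 rates of 12/66 and 18/48.
- **Reach.** Sections 11.2 and 11.3 carry the same analysis to Week 8 and to the exploratory clearance and 75%, 90% and 95% reduction endpoints.

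**The concern.** The inverse logit is a curve, so transforming an average log odds differs from averaging transformed log odds. Below 50% the curve bends upward, and the value at the covariate mean lies under the mean of the subjects' own probabilities. The subject to whom the SAP's value applies has mean age, mean lesion count, a fractional investigator type and a fractional household type.

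At stake are the only model-based absolute effect figures specified for the primary endpoint: the two adjusted proportions, their intervals, and the interval for their difference. A reader will take them as adjusted clearance rates and compare them with the crude rates, with Phase 2 and with the planning assumptions. Vehicle clearance, the reference for judging benefit, loses most in relative terms.

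**Working it through.** **1. The plan's own figure.** Inputs from Section 5: "227 subjects in the SB206 12% QD group and 113 subjects in the vehicle group", two-sided 0.05. With a pooled null variance,

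power = Φ[(d − 1.96·SE0)/SE1], where SE0 = √[p̄(1−p̄)(1/113 + 1/227)] and SE1 = √[pV(1−pV)/113 + pA(1−pA)/227].

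For 18% v 36%: p̄ = (113×0.18 + 227×0.36)/340 = 0.3002, SE0 = 0.05277, SE1 = 0.04818. Power = Φ[(0.18 − 0.1034)/0.04818] = Φ(1.59) = 94.4%. The other two scenarios give 93.4% and 82.8%. The SAP states 94%, 93% and 83%, so its figures reproduce, and they are built on subject proportions.

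**2. A case that can be checked by hand.** Suppose half the subjects sit 0.5 above the mean log odds and half 0.5 below (SD 0.5; an assumption).

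- Vehicle, mean log odds −1.596: the two probabilities are 25.05% and 10.95%. Their average is 18.0%; the value at the mean is expit(−1.596) = 16.9%.
- Active, mean log odds −0.611: 47.2% and 24.8%. Average 36.0%; value at the mean 35.2%.

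**3. Range over covariate strength.** Let s be the SD of the covariate part of the linear predictor. For each s, solve mean[expit(a + s·x)] = 18% or 36% for a, then read off expit(a). Four shapes of x were tried: normal, left-skewed and right-skewed (from lesion counts within 3–70), and a mixture. Both s and the shapes are assumptions.

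| s | Vehicle at mean (true 18%) | Active at mean (true 36%) | Difference at mean (true 18.0) |
|---|---|---|---|
| 0.25 | 17.7% | 35.8% | 18.1 |
| 0.5 | 16.9% | 35.1–35.5% | 18.1–18.6 |
| 1.0 | 14.2–14.4% | 32.4–34.7% | 17.9–20.5 |
| 1.5 | 11.0–11.5% | 28.6–34.3% | 17.1–22.9 |

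Both arms are low in every row. The difference has no fixed direction. Its lowest value comes from a left-skewed predictor, the shape that a right-skewed lesion count gives if more lesions mean less clearance; its highest comes from a right-skewed one.

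**4. Trials of 340.** In 600 simulated trials per setting (227/113, logistic fit with the SAP covariates, right-skewed lesion counts, subjects taken as independent):

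| s | Active: at mean / crude | Vehicle: at mean / crude | Both arms below crude |
|---|---|---|---|
| 0.24 | 35.4 / 35.8% | 17.5 / 18.1% | 77% |
| 0.48 | 34.9 / 36.0% | 16.8 / 18.1% | 94% |
| 0.95 | 32.4 / 35.9% | 14.0 / 17.7% | 99.7% |
| 1.43 | 29.0 / 35.9% | 11.5 / 18.0% | 100% |

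The prediction at the mean was below the standardised proportion in both arms in every trial. The standardised proportions matched the crude ones on average to within about 0.1 point.

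**5. Rates of 50% and above.** With a normal predictor and s = 1.0, a true 50% gives 50%, 60% gives 62% and 70% gives 73.5%. The shortfall vanishes and then reverses.

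**The case against.** **No inference changes.** In this model equal proportions means a zero treatment coefficient, so the stated hypothesis is properly tested. The odds ratio, its interval, the P-value and the fixed-sequence procedure in Section 10.7 do not depend on where predictions are evaluated. This stands in full.

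**The quantity is disclosed.** The SAP calls these predicted proportions and says where they are evaluated. That is true, but disclosure does not make them estimates of the proportion named in the hypotheses.

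**Crude rates may also appear.** Section 6 asks for frequencies and percentages of categorical variables, and Section 10.4 counts missing responses as nonresponse, so every ITT subject has an outcome. A reader might infer that the main table will show two conflicting rates side by side. The table shells are not in the documents, so that cannot be confirmed. Crude percentages would expose the gap; they would not correct the adjusted proportions or their intervals.

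**The size is assumed.** Also true. An odds ratio of 0.61 per 10 lesions, for example, implies 1/0.61^6.7 ≈ 27-fold odds between 3 and 70 lesions, and 0.45 implies about 210-fold; nothing in the documents supports either. With weak covariates the gap is far inside sampling error: binomial 95% half-widths at the planned rates are about 7 points on vehicle and 6 on active. Chance imbalance can then put one arm's prediction above its crude rate.

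**Conclusion.** The mismatch is real: the predicted proportions, and the interval for their difference, refer to a subject at the covariate mean, while the hypotheses and planning rates refer to the proportion of subjects. At the planned rates both arms are expected to come out low, by the amounts tabulated: a few tenths of a point at s = 0.25, about 1–4 points for s of 0.5–1.0, and up to about 7 at s = 1.5. These sizes rest on assumed covariate strengths and shapes. The trial simulations also ignored household correlation, which Section 5 puts below 10%.

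Three stronger readings are tempting and not supported:

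- That both arms' predictions must fall below the observed rates. This is an expectation that depends on covariate strength and on rates clearly below 50%. For endpoints near or above 50%, possibly the 75% reduction, the shortfall can vanish or reverse.
- That the difference is essentially untouched. This holds for weak covariates and for some shapes, but not generally.
- That the primary result is compromised. It is not.

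This is a free improvement to the reporting of absolute effects, not a fault in the primary test.

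**What to change.** In Section 11.1, keep the GEE fit and replace prediction at the covariate mean with standardisation. For every ITT subject, predict the probability of clearance once with treatment set to SB206 and once with vehicle, holding the subject's own covariates. Average each set over all ITT subjects. Report the two averages and their difference, with 95% intervals by the delta method from the robust, household-clustered covariance matrix, and place them beside the crude counts and percentages. The current standard-error formula for the difference would be replaced accordingly. Apply the same method at Week 8 and to the responder-type exploratory endpoints.

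The cost is a paragraph of SAP text and a few lines of code. The test, alpha, sample size, odds ratio and P-value stay as they are.

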11.2 Secondary Efficacy Analyses

The secondary endpoint of the proportion of subjects with complete clearance of all treatable MC at Week 8 will be analyzed in the same manner as the primary endpoint. A sensitivity analysis using the PP Population will be provided.

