11.3 Exploratory Analyses

The exploratory endpoints based on the proportion of subjects achieving complete clearance or 75%, 90%, or 95% reductions will be analyzed in the same manner as the primary endpoint.

Since the within-household correlation is expected to be small and the change and percent change from Baseline in the number of treatable MC are exploratory, they will be analyzed using a repeated measures mixed model for the respective visits with the same covariates as the primary model together with visits and treatment by visit; an unstructured covariance matrix will be utilized. If the calculation of the percent change from baseline is influenced by outliers with calculated values >100%, then the influence of outliers will be avoided for analysis by censoring them so that all values were in the range of -100% to 100%. If the model fails to converge, then other correlation structures will be explored.

Since the within-household correlation is expected to be small and time to first complete clearance of all MC is exploratory, it will be analyzed using Kaplan-Meier methods. The number and percentage of subjects achieving complete clearance, number and percentage of censored subjects, and Kaplan-Meier estimates of first quartile, median, and third quartile will be summarized by treatment group. Differences in Kaplan-Meier curves between the treatments will be tested for significance using a stratified log-rank test.

The proportion of subjects with scarring and the proportion of subjects with keloid or hypertrophic scarring will be summarized descriptively at each visit.

The change from Baseline of the composite score from age-matched (at Baseline) DLQI/CDLQI will be summarized descriptively and separately for each questionnaire. The scoring algorithms are detailed in [Appendix A](#). The CDLQI will be examined in the following Week 12 response categories: complete clearance, 95% reduction in lesion counts, 90% reduction in lesion counts, and subjects who did not achieve complete clearance. Additionally, the changes from Baseline in the following subscales: Symptoms and Feelings, Daily Activities, Leisure, Work and School, Personal Relationships, and Treatment, for DLQI, and Symptoms and Feelings, Leisure, School or Holidays, Personal Relationships, Sleep, and Treatment, for CDLQI, and each question will be summarized descriptively.

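### Final SAP 11.1: the legend for the risk-difference CI defines variance terms as standard errors and puts the last on the odds-ratio scale, making the interval about 2.0 to 3.2 times too wide at the planned effects

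*Combined protocol and SAP*

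**What the plan says.** This concerns the final SAP, the version that cites table shells Version 3.0. Section 11.1 adds to the odds-ratio results an interval for the absolute difference: "The difference in proportion confidence interval will be calculated using the following formula". The interval is the difference in predicted proportions plus or minus a normal quantile times an SE. The two proportions "are the transformed predicted log odds at the mean of the covariates". The SE combines the two arms' s² terms, and it recovers the covariance of the two predicted log odds as half of (s² for SB206 + s² for vehicle - s² for the odds ratio). The legend then says that the s² terms "are the standard errors of the predicted log odds and the odds ratio".

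Later in the same section, the dropout sensitivity analysis pools the "results for the estimated log odds ratio for treatment and its estimated standard error". There the log odds ratio is named correctly.

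The method carries over to other endpoints. Section 11.2 states that "Week 8 will be analyzed in the same manner as the primary endpoint", and section 11.3 states that "75%, 90%, or 95% reductions will be analyzed in the same manner as the primary endpoint".

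The formula appears neither in the protocol nor in the two earlier SAP versions, and section 14 of the final SAP does not list it as a change. No other text therefore settles what the symbols mean.

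**The concern.** The legend departs from what the formula needs in two ways.

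1. **Square.** A delta-method variance is built from variances. The legend equates s² with a standard error.
2. **Scale.** The covariance term comes from Var(X - Y) = Var(X) + Var(Y) - 2 Cov(X, Y), where X and Y are the two predicted log odds. X - Y is the log odds ratio, so the third quantity must be Var(log OR). Both the subscript and the sentence say odds ratio.

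A programmer who follows the definitions would report a wrong interval for the absolute difference, which is the scale on which the trial was sized. The main efficacy table could then show a clearly significant odds ratio beside a difference whose interval spans zero. The same would happen at Week 8 and for the percentage-reduction endpoints.

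**Working it through.** **Reading the formula.** In the text available here the SE is broken over two lines and looks like a fraction. I read it as one wrapped product; the break is an extraction artefact and not part of the concern. With a = p_S(1 - p_S) and b = p_V(1 - p_V) for SB206 and vehicle:

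SE = sqrt[ a²·s1 + b²·s2 - ab·(s1 + s2 - s3) ]

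**Inputs (SAP section 5).** 227 SB206 and 113 vehicle subjects; two-sided 0.05; planned rates 36% v 18%, 38% v 20% and 35% v 20%. The stated powers are 94%, 93% and 83%. A pooled-variance normal approximation gives 94.4%, 93.4% and 82.8%, so these inputs reproduce the plan's figures.

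**Assumption.** The arms are treated as unadjusted and uncorrelated, so Var(log odds) = 1/(n·p·(1 - p)) and the true covariance is 0.

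**Quantities at 36% v 18%.**
- a = 0.36 × 0.64 = 0.2304; b = 0.18 × 0.82 = 0.1476
- Var(log odds): 1/(227 × 0.2304) = 0.0191 and 1/(113 × 0.1476) = 0.0600; the SEs are 0.138 and 0.245
- Var(log OR) = 0.0191 + 0.0600 = 0.0791; SE 0.281
- OR = 2.5625; SE(OR) = 2.5625 × 0.2812 = 0.7206, which squared is 0.519
- Wald z on the log OR = 3.35, P = 0.0008

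**Readings of the legend.** A squares the SEs but leaves the last term on the OR scale. B leaves the SEs unsquared but uses the log OR. C is the legend exactly as written.

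| Reading | s1, s2, s3 | Implied covariance | SE | Ratio | 95% CI (points) |
|---|---|---|---|---|---|
| Correct | 0.0191, 0.0600, 0.0791 | 0 | 0.0482 | 1.0 | +8.6 to +27.4 |
| A | 0.0191, 0.0600, 0.519 | -0.220 | 0.1315 | 2.7 | -7.8 to +43.8 |
| B | 0.138, 0.245, 0.281 | +0.051 | 0.0960 | 2.0 | -0.8 to +36.8 |
| C | 0.138, 0.245, 0.721 | -0.169 | 0.1554 | 3.2 | -12.5 to +48.5 |

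The correct row equals the ordinary unpooled SE, which confirms the form of the expression.

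**The other two planned effects.**

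| Rates (P) | Correct | A | B | C |
|---|---|---|---|---|
| 38% v 20% (0.0010) | +8.3 to +27.7 | 2.6×: -7.1 to +43.1 | 2.0×: -1.4 to +37.4 | 3.2×: -12.8 to +48.8 |
| 35% v 20% (0.005) | +5.4 to +24.6 | 2.3×: -6.7 to +36.7 | 2.0×: -4.1 to +34.1 | 2.9×: -13.4 to +43.4 |

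**Clustering.** With the SAP's bounds (intra-cluster correlation below 10%, mean household size about 1.3), the design effect is at most about 1 + 0.3 × 0.1 = 1.03. The ratios become 1.97 to 3.20, every faulty interval still includes zero, and the largest P is 0.0057.

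**Check in the planned GEE.** I used 1000 simulated trials with 227 and 113 subjects, mean household size 1.3 and at-mean rates of about 36% v 17%. I assumed no within-household correlation and a lesion-count slope of -0.02 per lesion. With log-scale variances, the formula matched the direct delta-method SE to within 2 × 10⁻¹⁷. Median inflation was 2.9× (A), 2.0× (B) and 3.3× (C). Among the 95.1% of trials with P < 0.05, the interval included zero in 0% (correct), 100% (A), 49% (B) and 100% (C).

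**Dependence on the effect.** Reading A gives 1.8× at 30% v 20%, 1.3× at 25% v 20%, 1.0× when OR = 1, and 0.73× (too narrow) at 15% v 20%. Readings B and C both give 1.9× at 20% v 20%.

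**The case against.** The strongest reply is that the symbol carries an exponent, so any statistician would take s as the standard error and s² as its square. The p(1 - p) factors and the covariance bracket also signal that log-odds variances are meant. This is a fair answer to readings B and C, but it does not remove the scale error. Squaring the standard error of the odds ratio, as the subscript and the sentence direct, is reading A, which is 2.3 to 2.7 times too wide at the planned effects and still includes zero.

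A second reply is that inclusion of zero is fragile under B. That is right. At the Phase 2 rates (37.5% v 18.2%) with 227 and 113 subjects, B gives +0.3 to +38.3 points. With an assumed correlation of 0.2 between the predicted log odds, B at 36% v 18% gives +0.1 to +35.9, while C still gives -11.0 to +47.0. The statement that every reading includes zero therefore holds at the three planned effects under the stated assumptions, and more generally only for the OR-scale readings.

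Third, Appendix C requires independent reprogramming and senior review, and an interval spanning zero beside P = 0.0008 would be conspicuous. Review may well catch it. Two programmers working from the same legend could nevertheless agree on the same wrong number.

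Finally, this interval is supplementary and no success criterion uses it. That stands, and it limits the severity.

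**Conclusion.** The concern holds. The expression is right and the definition of its inputs is wrong, both in the missing square and in the scale of the last term. At the three planned effects the interval is 2.0 to 3.2 times too wide across the possible readings (2.9 to 3.2 for the legend exactly as written). All nine faulty intervals include zero while P runs from 0.0008 to 0.005.

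These figures rest on unadjusted, uncorrelated arms at the planned sample size; the simulated GEE gave similar inflation. The size varies with the true effect, and reading A can even give too narrow an interval when SB206 does worse than vehicle. If programmers silently use log-scale variances, the output is correct.

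The consequence is confined to the reported interval for the difference in proportions, at Week 12 and wherever the same method is reused. The correction should be made, but no conclusion of the primary test depends on it.

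**What to change.** In section 11.1 of the final SAP, replace the legend with a statement that each s² is the squared standard error (variance) of the corresponding predicted log odds and, for the last term, of the log odds ratio for treatment. Relabel the last subscript from the odds ratio to log(OR). Sections 11.2 and 11.3 inherit the correction by reference.

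The cost is one sentence and one subscript. Data collection, sample size, the GEE test and the testing sequence do not change.

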8.3 Method of Assigning Subjects to Treatment Groups

In this randomized, double-blind, vehicle-controlled study, subjects who meet study entry criteria will be randomly assigned in a 2:1 ratio (active: vehicle). The randomization schedule will be computer generated using a permuted block algorithm and will randomly allocate IP to randomization numbers. The randomization numbers will be assigned sequentially through a central IWRS as subjects are entered into the study. At randomization, subjects will be stratified into four strata corresponding to the cross-classification of household number of randomized subjects (1 subject per household vs 2 subjects per household) and investigator type (dermatologist vs other). Households randomizing 2 subjects would receive the same treatment assignment for both subjects. Approximately 340 subjects, 6 months of years of age and older, with a minimum of 3 and a maximum of 70 lesions at Baseline will be randomized.

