6. GENERAL ANALYSIS CONSIDERATIONS

The statistical analyses will be reported using summary tables, listings, and figures (TLFs). The International Council for Harmonisation (ICH) numbering convention will be used for all TLFs. Unless otherwise noted, all statistical testing will be 2-sided and will be performed at the 0.05 significance level. Tests will be declared statistically significant if the calculated *P*-value is ≤ 0.05 .

Continuous variable summaries will include the number of subjects (n) with non-missing values, mean, standard deviation (SD), median, minimum, and maximum. Other statistics such as quartiles, confidence intervals (CIs), and number of missing values may be added as appropriate.

Categorical variable summaries will include the frequency and percentage of subjects who are in the category or each possible value. In general, the denominator for the percentage calculation will be based upon the total number of subjects in the study population within each treatment group, unless otherwise specified. The denominator for by-visit displays will be the number of subjects in the relevant study population with non-missing data at each visit.

All summary tables will be presented by treatment group. Baseline summaries will also include an overall summary column.

Individual subject data obtained from the eCRFs and any derived data will generally be presented by subject in data listings. Additionally, a listing of the subjects requiring a narrative because they experience one of the following events: serious adverse event, death, discontinued the study due to an AE, hypertrophic or keloid scarring, unresolved scars, or LSR suggestive of allergic contact dermatitis will be presented.

The analyses described in this plan are considered a priori, in that they have been defined prior to breaking the blind.

Any analyses performed subsequent to breaking the blind will be considered post hoc and exploratory. Post hoc analyses will be labeled as such on the output and identified in the clinical study report.

All analyses and tabulations will be performed using SAS® software Version 9.4 or higher. Tables, listings, and figures will be presented in RTF format.

The process for SAS program validation and quality control (QC) for programs and outputs is documented in the Synteract working instruction “SAS programming quality control.” Study-specific QC requirements can be found in [Appendix C: SAS Programming QC Requirements](#).

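### The one-subject-per-household sensitivity model omits household number, a randomization stratum and primary-model covariate that still varies in the subset

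*Combined protocol and SAP*

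**What the plan says.** Protocol 8.3 sets the randomization strata: "At randomization, subjects will be stratified into four strata corresponding to the cross-classification of household number of randomized subjects", crossed with investigator type. Two subjects from one household go to the same arm. The primary GEE in SAP 11.1 adjusts for both stratification factors, age and baseline lesion count.

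The same section adds a sensitivity analysis in a subset of the ITT Population, "where only 1 subject from each household is chosen to contribute to the model". The member with the most treatable lesions at baseline is kept, and the older one if counts tie. The model is then given: "A logistic regression model including treatment, investigator type, age, and baseline lesion counts will be utilized". Investigator type is kept and household number is not, and no reason is stated.

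Four other places bear on this:

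- SAP 10.3 removes a stratification factor from the primary efficacy model only when a level has fewer than 3 responders or non-responders, or when there are fewer than 10 of either.
- SAP 10.8 keeps household number in its pooled-center logistic model.
- SAP 11.3 gives the mixed models for lesion counts the primary model's covariates.
- SAP 5 expects an intra-cluster correlation below 10% and an average household size capped at roughly 1.3.

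**The concern.** Household number can look redundant once each household supplies one subject. It is not. A subject kept from a two-subject household was still randomized in the two-subject stratum, so both levels remain.

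The analysis is evidently meant to show whether the primary result depends on having two subjects from some households. For that comparison the covariates should match the primary model. With a logit link, leaving out a prognostic covariate moves the conditional odds ratio toward the null even under perfect balance, so the two odds ratios would not estimate quite the same quantity. What is at stake is how cleanly one supportive analysis can be compared with the primary one.

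**Working it through.** **1. The plan's own power figure.** Inputs from SAP 5 and 6: "227 subjects in the SB206 12% QD group and 113 subjects in the vehicle group"; "all statistical testing will be 2-sided and will be performed at the 0.05 significance level"; 18% on vehicle against 36% on SB206.

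Pooled two-proportion test: power = Φ[(d − 1.96·SE0)/SE1].

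- Mean rate = (113×0.18 + 227×0.36)/340 = 0.300
- SE0 = √[0.300×0.700×(1/113 + 1/227)] = 0.0528
- SE1 = √[0.18×0.82/113 + 0.36×0.64/227] = 0.0482
- Power = Φ(1.59) = 94.4%, against 94% stated

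The other two scenarios give 93.4% and 82.8%, against 93% and 83% stated. The figures reproduce.

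**2. Does household number still vary?**

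- Households: 340/1.3 ≈ 262
- Two-subject households: 340 − 262 = 78, or 30%
- One-subject households: 262 − 78 = 184

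At the planning rates the average response is 0.30, so the two-subject level would hold about 78×0.30 ≈ 23 responders and 55 non-responders. With household odds as low as 0.22 times those of one-subject households (roughly 0.22×0.30/0.70 = 0.094, a rate of 8.6%), it would hold about 7 responders. The sparse-cell rule would not be expected to remove the term.

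**3. Size of the omission by formula.** Suppose the two-subject stratum has half the odds of clearance (an assumption).

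- Variance of the omitted term = 0.693²×0.3×0.7 = 0.10
- Attenuation factor ≈ 1/√(1 + 0.346×0.10) = 0.983
- Treatment log odds ratio at 18% vs 36% = ln 2.5625 = 0.941
- Shift ≈ 0.017×0.941 = 0.016

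The 1.3 is described as a cap, so 30% is near a ceiling. At an average of 1.1 the two-subject share is 10% and the attenuation is about 0.7%.

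**4. Size by simulation.** There were 184 one-subject and 78 two-subject households, 2:1 permuted blocks in the four strata, a treatment odds ratio of 2.56, and 2,500 trials per setting. These assumptions are not in the documents: the household effects, block size 3, an equal investigator-type split, and the effects of age, lesion count and investigator type. In two-subject households the lesion count was the larger of two draws.

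| Household OR (2 vs 1) | Mean log OR, without | With | Shift | Power %, without | With |
|---|---|---|---|---|---|
| 0.22 | 0.948 | 0.991 | 0.043 | 78.0 | 79.6 |
| 0.37 | 0.951 | 0.977 | 0.026 | 80.8 | 81.8 |
| 0.61 | 0.966 | 0.977 | 0.011 | 83.7 | 84.1 |
| 1.00 | 0.980 | 0.984 | 0.004 | 87.9 | 88.0 |
| 1.65 | 0.957 | 0.970 | 0.013 | 88.7 | 89.0 |
| 2.72 | 0.930 | 0.975 | 0.045 | 88.9 | 89.7 |

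The shift is the difference between the two models fitted to the same trials. Most of these means lie slightly above the simulated 0.941, so the shift is not bias against the true value. With no treatment effect, rejection was 4.4% to 5.5% without the term and 4.4% to 5.6% with it (Monte Carlo error about 0.4 points).

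**5. For scale.** With about 175 and 87 subjects, the unadjusted standard error of the log odds ratio is √[1/(175×0.36×0.64) + 1/(87×0.18×0.82)] ≈ 0.32. The largest shift is 0.045/0.32 ≈ 14% of that. Moving from 340 to 262 subjects lowers unadjusted power from 94.4% to 87.2%, far more than the missing term does.

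**The case against.** The strongest reply is that this is a small mismatch in a supportive analysis. The primary estimate and alpha are untouched. Household number is in the primary model and is a forest-plot subgroup in SAP 10.6. SAP 10.3 itself allows the factor to be dropped. The variables used to choose the sibling, lesion count and age, are both in the model. All of this stands and limits the size of the point. None of it explains the omission: the rule in 10.3 is conditional and written for the primary model, whereas here the term is left out unconditionally.

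Three stronger readings are tempting, and the documents do not support them.

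- *The analysis is not as randomized.* The subset comes from the ITT Population, where SAP 8 assigns treatment as randomized. Siblings share an arm and selection uses baseline data only. Simulated type I error is not inflated.
- *The standard error is wrong because it ignores the stratification.* Investigator type is retained and error rates are nominal. In the simulation with a treatment effect, the average standard error was slightly larger with the term (0.308 to 0.365, against 0.300 to 0.358). The small power gain comes from the larger estimate.
- *The missing term is what prevents a difference from the primary result being put down to clustering.* Restoring it would not isolate clustering either, because about 78 subjects are dropped and the sibling with more lesions is kept. That change of sample is the larger difference. The move from GEE to ordinary logistic regression adds little: with clusters of size 1 the estimating equation is the same, and only model-based against robust standard errors may differ.

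**Conclusion.** The point holds as a minor inconsistency. The model omits one of the two stratification factors, although that factor still has two well-filled levels and the SAP keeps it in comparable models. The treatment comparison remains valid. Over assumed household odds ratios of 0.22 to 2.72, the cost is about 0.004 to 0.045 on the treatment log odds ratio and at most about 1.6 points of power. With no household effect the shift is negligible. The sizes rest on the SAP's average of 1.3 and on household and covariate effects that the documents do not give. No conclusion from the primary analysis depends on this.

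**What to change.** In SAP 11.1, add the number of subjects randomized in the household (1 vs 2) to the covariates of the one-subject-per-household logistic model, and state that the sparse-cell rule of SAP 10.3 applies to it. The covariates then match the primary GEE. If the omission is deliberate, give the reason instead. When the result is reported, note that the subset is smaller and made up of the household members with the most lesions, so it may differ from the primary result for that reason alone.

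The cost is one term in one sentence. The variable is already needed for the primary model, and nothing changes in data collection, sample size or alpha. The change should be made before unblinding, since SAP 6 classes later analyses as post hoc.
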